## SAP Change History

Changes Made	
V1.0.0	Initial Version dated 23 April 2017
V1.1.0	
Section 2.1: Blinded Treatment Period: Maximum of 18 weeks. Open Label Extension Period: Subjects will be offered open label therapy when the subject completes 18 weeks of blinded drug therapy. All subjects must have completed all assessments in Part 1 and remain on blinded treatment until week 18 before proceeding to Part 2. Section updated as per protocol amendment 3.
 
Section 7.3: As primary analysis is MMRM, no imputation will be performed. Text updated to remove imputation proposal for primary analysis. & Imputation Rules added for 6MWD data for sensitivity analysis with ANCOVA model. Section updated as per FDA recommendations and Protocol amendment 3.
 
Section 7.3: Additional clarification for imputation rule for subjects who die. All subjects who die will have zero 6MWD imputed for missing data. Section updated as per FDA recommendations and Protocol amendment 3.
 
All analysis proposed for other efficacy endpoints changed to ANCOVA, considering planned LOCF imputation for other endpoints

## 1.0 Objective and Statistical Analysis Plan

This Statistical Analysis Plan (SAP) describes the planned analyses to support completion of the Clinical Study Report (CSR) for protocol PULSE-PAH-004 entitled “A Phase 3, Placebo Controlled, Double-Blind, Randomized, Clinical Study to Determine the Efficacy, Safety and Tolerability of Pulsed, Inhaled Nitric Oxide (iNO) Versus Placebo in Symptomatic Subjects with Pulmonary Arterial Hypertension (PAH): INOvation-1”.

This SAP is based on the following study document:

- Original Protocol, 25th August 2015
- Amendment 1, 11th Jan 2017
- Amendment 2, 21st April 2017
- Amendment 3 dated 7th June 2017.

## 2.0 Introduction

Pulmonary arterial hypertension is a progressive disease characterized by progressive pulmonary vascular arteriopathy leading to elevation in pulmonary vascular resistance (PVR) and pulmonary arterial pressure (PAP) with right ventricular failure and death if untreated ([McLaughlin 2009](#); [Barst 2009](#); [McGoon 2009](#); [Badesch 2007](#)).

The overall current 5-year survival with current standard of care is only 60% ([Benza 2010](#)).

There is no cure for PAH and the 5-year survival rate for idiopathic or heritable PAH was approximately 30% prior to the availability of targeted PAH therapies based on Registry data from the 1980s ([Anderson 2010](#)).

Currently approved treatments have been demonstrated to have both short- and long-term efficacy ([McLaughlin 2006](#); [Barst 2009](#); [McGoon 2009](#); [Badesch 2007](#); [Anderson 2010](#); [Ghofrani 2013](#)). These include:

- Synthetic prostacyclin, i.e., epoprostenol,
- Prostacyclin analog,
- Treprostinil or Iloprost;
- Endothelin receptor antagonist (ERA), i.e., bosentan, ambrisentan, or macitentan;
- Phosphodiesterase type-5 (PDE-5) inhibitors, i.e., sildenafil and tadalafil;
- Soluble guanylate cyclase (sGC) stimulators, i.e., riociguat

These medications may improve symptoms, exercise capacity, and clinical outcome, but may be limited by either parenteral delivery system, the need for frequent laboratory monitoring, frequent dosing schedules, or unwanted side effects.

Because of the availability of several agents working via different mechanisms, interest is developed in add on (i.e., combination) therapy. This strategy has proven successful in improving clinical outcomes in

some subjects. Yet, as stated above, despite these significant advances in the treatment of PAH, the current 5-year survival for Group 1 PAH is ~60% utilizing the available approved PAH therapies (Anderson 2010). Patients who are receiving prostacyclin therapy, ERA, and PDE-5, have no further treatment options other than atrial septostomy and lung transplantation.

PAH is associated with impaired release of nitric oxide at least in part because of reduced expression of nitric oxide synthase in the vascular endothelium of pulmonary arteries (McLaughlin 2009; Barst 2009; McGoon 2009; Badesch 2007; Anderson 2010). Thus, chronic administration of iNO may be viewed as replacement therapy in some subjects with PAH making it a logical choice for clinical evaluation.

Overall, review of the published medical literature and clinical experience indicates that iNO at doses of 0.013 to 0.1 mg/kg per hour for up to 2 years appears safe and suggests efficacy for the treatment of pulmonary hypertension (PH).

Inhaled NO offers an additional treatment option for patients, in particular patients who are already receiving prostacyclin therapy, ERA, and PDE-5, who have no other medical treatment options. Inhaled NO has the advantage of being able to be added to all other available PAH therapies excluding riociguat.

Bellerophon Pulse Technologies recently completed a Phase 2 clinical trial of iNO/INOpulse for PAH in the United States and Canada (Study IK-7001-PAH-201).

The key inclusion criteria for subjects in this trial were: pulmonary hypertension WHO Group I, on at least one other PAH medication for at least 12 weeks prior to treatment with iNO/INOpulse, and demonstrated ability to walk between 100 and 450 meters within 6 minutes.

In Part 1 of the placebo-controlled, double-blind clinical trial, 80 subjects were randomized in a 1:1:1 fashion to placebo or to one of two active iNO doses—25 or 75 mcg/kg IBW/hr for 16 weeks. Subjects who completed Part 1 of the trial were able to enrol in an open-label, long-term extension portion of the study (Part 2), in which all subjects received one of the two iNO doses. The objective in Part 2 was to explore the long-term safety and tolerability of therapy.

The primary endpoint of Part 1 was change in pulmonary vascular resistance (PVR) from baseline at 16 weeks, and the main secondary endpoint was change in placebo-adjusted 6-minute walk distance (6MWD) over the same period.

The baseline characteristics seemed to indicate that subjects in the iNO groups had more severe disease. LTOT use at baseline was 78% and 59% in the 75 and 25 mcg/kg IBW/hr cohorts, respectively, compared to 46% in the placebo cohort. Baseline PVR values were higher in the higher dose group, and 6MWDs were lower in the same group. The results in the ITT population showed a trend toward a lowering of PVR with iNO treatment and an increase in 6MWD, but this did not reach statistical significance.

Inhaled NO was relatively well-tolerated in Part 1 of the trial. More serious adverse events (SAEs) occurred in the 75 mcg/kg IBW/hr dose group (9 events) versus the 25 mcg/kg IBW/hr and placebo groups (4 events each). The excess AEs were related to the respiratory system. All AEs related to the respiratory system will be adjudicated in the Phase 3 trials by an Independent Clinical Events Committee (ICEC).

Eighty-one percent of subjects elected to enter into the long-term extension trial.

The purpose of this phase III clinical trial is to explore iNO on patients with LTOT.

Subjects with LTOT are more likely to be compliant and may have better outcomes. In this Phase 3 trial, recruitment will be limited to only subjects on LTOT. For the indication of PAH, iNO is being developed as a drug/device combination therapy to be used with the INOpulse delivery device.

The INOpulse device is a complete, integrated system that uses a 0.074 liter aluminum cartridge containing a concentration of 6.0 mg/L (4880 ppm) of NO gas. The device is lightweight and portable, allowing NO to be administered via a nasal cannula to spontaneously breathing subjects. These features make it ideal for use in an ambulatory setting. The main advantage of the INOpulse device for spontaneously breathing subjects lies in its ability to deliver precise, preset NO doses over time, independent of the subject's respiration rate and tidal volume. Prescribed doses of iNO are delivered through the INOpulse according to amount of drug per ideal body weight (IBW) per hour (i.e., mcg/kg IBW/hr). The iNO dose is pulsed over the first half of the subject's inspiration rather than inhaled throughout the entire inspiratory period and the hourly set dose is accurately delivered throughout the hour.

The primary objective in this study is to evaluate the efficacy of iNO on exercise using 6-minute walk distance (6MWD) in subjects with PAH currently receiving background PAH medication and LTOT.

## 2.1 Study Details

This is a multi-center, randomized, double-blind, placebo-controlled, parallel-group design to determine the efficacy, safety and tolerability of pulsed iNO versus placebo in symptomatic subjects with PAH currently receiving background PAH medication and LTOT (long term oxygen therapy).

This study has two parts as follows:

- Part I: Blinded Treatment Period (Maximum of 18 weeks).
- Part II: Open label (Subjects will be offered open label therapy when the subject completes 18 weeks of blinded therapy)

All subjects must complete Part I, at least 18 weeks of blinded treatment before open label therapy is offered.

After the Screening period, the subjects will be randomized at Week 0 to enter the double blind and run-in period (Week 0 to Week 2) to assess their eligibility to continue in the study by their usage of the INOpulse device for an average  $\geq 16$  hours (rounded to the nearest hour) per day with no more than 2 days of usage  $< 8$  hours per day.

Those subjects not meeting the 12 hour INOpulse device usage requirement (by Week 2) will be discontinued and ineligible to proceed to the next phase of treatment.

Subjects will be randomized to a treatment assignment as described in [Table 1](#) below. Subjects randomized to active iNO will receive a reduced dose of iNO during run in and subjects randomized to placebo will receive placebo during run in.

**Table 1: Dosing Assignments for Run-in, Treatment Periods and Open Label**

Cohort	Part I Blinded Treatment Period		Part II Open Label
	Run-in Period Week 0 to Week 2	Treatment Period Week 3 to Week 18	Open Label Treatment
Cohort 1: Placebo	Placebo at a dose setting of 15 mcg/kg IBW/hr	Placebo at a dose setting of 75 mcg/kg IBW/hr	iNO 75 mcg/kg IBW/hr
Cohort 2: iNO 75	iNO 15 mcg/kg IBW/hr	iNO 75 mcg/kg IBW/hr	iNO 75 mcg/kg

	Part I Blinded Treatment Period		Part II Open Label
Cohort	Run-in Period Week 0 to Week 2	Treatment Period Week 3 to Week 18	Open Label Treatment
mcg/kg IBW/hr			IBW/hr

Note: Study drug is dosed according to IBW and not actual body weight. IBW is determined by a subject's sex and height, and therefore will not change during the study period.

## 2.2 Protocol Amendments

Original protocol dated 25th August 2015, Amendment 1, Amendment 2 and Amendment 3 dated 11th Jan 2017, 21st April 2017 and 7th June 2017 respectively were used to develop this SAP.

## 3.0 Study Objectives

### 3.1 Part I Blinded Treatment Period

#### 3.1.1 Primary Objective

The primary objective in this study is to evaluate the efficacy of iNO on exercise using 6-minute walk distance (6MWD) in subjects with PAH currently receiving background PAH medication and LTOT.

#### 3.1.2 Secondary Objectives

The secondary objectives in this study are:

- To evaluate the time to clinical worsening (TTCW)
- To evaluate change in World Health Organization (WHO) Functional Class

#### 3.1.3 Tertiary Objectives

The tertiary objectives in this study are:

- To evaluate changes in health-related quality of life using the Short Form-36 (SF-36) version 2 health survey
- To evaluate the impact of iNO on pulmonary hemodynamics in a subset of subjects
- To evaluate the changes in right ventricular (RV) and left ventricular (LV) function as measured by echocardiography, in a subset of subjects
- To evaluate change in N-terminal of the prohormone brain natriuretic peptide (NT-proBNP)
- To evaluate change in Borg dyspnea score immediately following 6-minute walk test (6MWT)
- To evaluate change in 6MWD as related to degree of correlation between drug adherence and clinical efficacy measurement
- To evaluate subjects with unsatisfactory clinical response

- To evaluate the impact of iNO on frequency of heart-lung or lung transplantation, and deaths while awaiting transplantation
- To evaluate the impact of iNO on medical resource utilization

### 3.1.4 Safety Objectives

The safety objectives in this study are to evaluate the safety and tolerability of iNO.

## 3.2 Part II Open Label

### 3.2.1 Primary Objective

To evaluate the long term safety and tolerability.

### 3.2.2 Secondary Objective

To evaluate the change in exercise tolerance in subjects who switch from placebo to active therapy.

## 4.0 Study Endpoints

### 4.1 Primary Efficacy endpoint

6-minute walk distance (6MWD) is the primary endpoint for this study. This primary endpoint is collected at all the visits. Baseline for analysis of 6MWD is the Week 2 (Visit 2 assessments), average for two assessments at Week 2.

The change in 6MWD from baseline to 18 weeks (Table 2) is of primary interest.

**Table 2: Change in 6MWD from Baseline to 18 Weeks**

Variables	Module	Source of Data	Baseline Definition	Variable specific derivation	Change from Baseline analysis
6MWD	Six Minute Walk Test (SMWT)	CRF	Average of two Week 2 (V2) Assessment	No, CRF data.	Yes

For open label period, Change in 6MWD from Baseline (week 2) and from week 18 will be analysed at month 4, 8 and 12.

### 4.2 Secondary Efficacy Endpoints

The secondary endpoint in this study includes:

1. Time (in days) to first clinical worsening event (TTCW) measured from baseline to end of treatment period (Week 18).

Where clinical worsening events are defined (Table 3 and Table 4) as follows:

**Table 3: Clinical Worsening Event**

Criteria #	Description
1	Death (all-cause mortality)
2	Atrial septostomy
3	Hospitalization due to worsening of PAH (adjudicated)
4	Start of new specific PAH treatment (endothelin receptor antagonists [ERAs], phosphodiesterase type-5 [PDE-5] inhibitors or prostanoids), an increase in the dose of an ERA or PDE-5, increase in the dose or frequency of an inhaled prostanoids, or an increase in the dose of an intravenous or subcutaneous prostanoids by >10%.
5	Decrease of >15% from baseline or >30% compared with the last study related measurement in 6MWD should be confirmed by a repeat measurement performed at least 14 days later.
6	Worsening of WHO Functional Class (e.g., from Class II to Class III or IV, OR Class III to Class IV); and should be confirmed by a repeat assessment at least 14 days later.

**Table 4: Time Clinical Worsening Event Derivation**

Variables	Module	Source of Data	Derivation	Comments (to be removed later)
All-cause mortality	End of Therapy Status SAE	CRF	One-One mapping	Standard binary field
Atrial septostomy	End of Therapy Status	CRF	One-One mapping	Standard Binary field
Hospitalization due to worsening of PAH (adjudicated)	Adjudication Module	Non CRF	One-One mapping	Standard Field
New PAH treatment	PAH specific therapies	CRF	One-One mapping	Refer to new PAH Therapy Module
Decrease of >15% from baseline or >30% compared with the last study related measurement in 6MWD should be confirmed by a repeat measurement performed at least 14 days later	6 minute walk test	CRF	
1) Decrease of >15% from Baseline
 
Or
 
2) Greater than 30% compared with baseline
 
And
 
3) should be confirmed by repeat
	
Points (1) and (2) are simple derivations ;
 
Point (3) is linked to visit window mapping, so be careful.

Variables	Module	Source of Data	Derivation	Comments (to be removed later)
			measurement performed at least 14 days	
Worsening of WHO Functional Class (e.g., from Class II to Class III or IV, OR Class III to Class IV); and should be confirmed by a repeat assessment at least 14 days later	WHO functional class assessment done at every visit, choose only post baseline	CRF	(1) Class II to class III (2) Class III to class IV (3) Confirmation by repeat assessment at least 14 days later	Points (1) and (2) are simple derivations ;  Point (3) is linked to visit window mapping, so be careful.

2. Change in World Health Organization (WHO) Functional Class (Table 5 and Table 6) from baseline to 18 weeks

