7.1.2. Secondary Endpoints

The secondary endpoints include:

1. TTCW, the time (in days) from start of treatment to first event (first day the event is noted), with iNO as compared to placebo, measured from baseline to 18 weeks. TTCW event is defined as any of the following:
 - a. Death (all-cause mortality)
 - b. Atrial septostomy
 - c. Hospitalization due to worsening of PAH (adjudicated)
 - d. Start of new specific PAH treatment (endothelin receptor antagonists [ERAs], phosphodiesterase type-5 [PDE-5] inhibitors or prostanoids), an increase in the dose of an ERA or PDE-5, increase in the dose or frequency of an inhaled prostanoids, or an increase in the dose of an intravenous or subcutaneous prostanoids by >10%.
 - e. Decrease of >15% from baseline or >30% compared with the last study related measurement in 6MWD should be confirmed by a repeat measurement performed at least 14 days later
 - f. Worsening of WHO Functional Class (e.g., from Class II to Class III or IV, OR Class III to Class IV); and should be confirmed by a repeat assessment at least 14 days later
2. Change in WHO Functional Class, with iNO as compared to placebo, from baseline to 18 weeks

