7.1.3. Tertiary Endpoints

The tertiary endpoints in this study include:

1. Change in health-related quality of life (using SF-36 version 2 health survey), with iNO as compared to placebo, from baseline to 18 weeks
2. Change in pulmonary hemodynamics (i.e., cardiac output [CO], cardiac index [CI], mean pulmonary artery pressure [mPAP], mean pulmonary capillary wedge pressure [mPCWP], systolic pulmonary artery pressure [sPAP], diastolic pulmonary artery pressure [dPAP], pulmonary vascular resistance [PVR], oxygen saturation by pulse oximeter [SpO₂], mixed venous O₂, and right atrial pressure [RAP]), measured by right heart catheterization (RHC), with iNO as compared to placebo, from baseline to 18 weeks, in a subset of subjects (approximately 50), at selected sites
3. Change in echocardiogram measurements right ventricular function (including right ventricular fractional area change, systolic pulmonary artery pressure [sPAP], tricuspid

annular motion/tricuspid annular plane systolic excursion, tricuspid annular systolic velocity, and Tei index) and left ventricular function (including left ventricular ejection fraction [LVEF], LV size, and improvement in LV early diastolic relaxation velocity), with iNO as compared to placebo, from baseline to 18 weeks, in a subset of subjects (approximately 50), at selected sites

4. Change in NT-proBNP, with iNO as compared to placebo, from screening to 18 weeks
5. Change in Borg dyspnea score immediately following 6MWT, with iNO as compared to placebo, from baseline to 18 weeks
6. Change in 6MWD as related to degree of drug adherence, with iNO as compared to placebo, from baseline to 18 weeks
7. The number of subjects with unsatisfactory clinical response, with iNO as compared to placebo, from baseline to 18 weeks. Defined as: WHO Functional Class III or IV symptoms with no improvement in 6MWD
8. Number of subjects undergoing heart-lung or lung transplantation, number of subjects listed for transplantation, and deaths while awaiting transplantation, from baseline to 18 weeks
9. Medical resource utilization, with iNO as compared to placebo, from baseline to 18 weeks

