16.3.2. Secondary Efficacy Endpoints

The secondary efficacy endpoints include:

1. TTCW*: The time (in days) from start of treatment to first event (first day the event is noted), with iNO as compared to placebo, measured from baseline to week 18. TTCW event is defined as any of the following:
 - a. Death (all-cause mortality)
 - b. Atrial septostomy
 - c. Hospitalization due to worsening of PAH (adjudicated)
 - d. Start of new specific PAH treatment (endothelin receptor antagonists [ERAs], phosphodiesterase type-5 [PDE-5] inhibitors or prostanoids), an increase in the dose of an ERA or PDE-5, increase in the dose or frequency of an inhaled prostanoids, or an increase in the dose of an intravenous or subcutaneous prostanoids by >10%.
 - e. Decrease of >15% from baseline or > 30% compared with the last study related measurement in 6MWD and should be confirmed by a repeat measurement performed at least 14 days later
 - f. Worsening of WHO Functional Class (e.g., from Class II to Class III or IV, OR Class III to Class IV); and should be confirmed by a repeat assessment at least 14 days later
2. Change in WHO Functional Class, with iNO as compared to placebo, from baseline to 18 weeks.

The TTCW endpoint will be analyzed with log-rank test stratified by the prostanoid usage status. The censoring time points for the analyses include the time points at which subjects drop out of the study or complete the study without any of the specified events.

The WHO Functional Class endpoint will be analyzed with the same method as that for the primary endpoint. Change from baseline to week 18 will also be evaluated as an exploratory analysis.

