**VII. Clinical Response:**

Number of subjects with unsatisfactory clinical response (Table 14), (WHO Functional Class III or IV symptoms with no improvement in 6MWD), with iNO as compared with Placebo, from baseline to 18 weeks.

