**Table 14: Clinical Response**

Variables	Module	Source of Data	Variable specific derivation	Combined Derivation
WHO Functional Class Status	WHO Functional Class assessment	CRF	No, CRF data.	At week 18 WHO status is III or IV.
6MWD	Six Minute Walk Test (SMWT)	CRF	No, CRF data.	1) Decrease of >15% from baseline Or 2) Greater than 30% compared with baseline And should be confirmed by repeat measurement performed at least 14 days

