### Table 26: Summary of Clinical Worsening Analysis

Variable	Model	Population	Factors
Time to clinical Worsening	Log Rank	ITT	Treatment Group and stratification by Prostanoid usage.
Time to clinical Worsening	Log Rank	mITT	Treatment Group and stratification by Prostanoid usage.
Time to Death (All-cause mortality)	Log Rank	ITT	Treatment Group and stratification by Prostanoid usage.
Time to Atrial septostomy	Log Rank	ITT	Treatment Group and stratification by Prostanoid usage.
Time to Hospitalization due to worsening of PAH (Adjudicated)	Log Rank	ITT	Treatment Group and stratification by Prostanoid usage.
Time to PAH specific therapy	Log Rank	ITT	Treatment Group and stratification by Prostanoid usage.
Time to decrease in Decrease of >15% from baseline or >30% compared with the last study related measurement in 6MWD	Log Rank	ITT	Treatment Group and stratification by Prostanoid usage.
Time to Worsening of WHO Functional Class (e.g., from Class II to Class III or IV, OR Class III to Class IV)	Log Rank	ITT	Treatment Group and stratification by Prostanoid usage.

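### SAP Tables 4 and 14 derive the 6MWD parts of clinical worsening and of unsatisfactory response by rules that contradict the endpoint definitions

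*SAP*

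**What the plan says.** **Clinical worsening.** Protocol 7.1.2 (item 1e) gives two 6MWD limbs. The first is a fall against baseline of more than 15%. The second limb is worded "or >30% compared with the last study related measurement in 6MWD should be confirmed by a repeat measurement performed at least 14 days later". Protocol 16.3.2 has the same reference value ("compared with the last study related measurement in 6MWD and should be confirmed by a repeat measurement"). So do SAP Table 3 (">30% compared with the last study related measurement in 6MWD"), SAP 7.4.1, and the component analysis in SAP Table 26 ("Time to decrease in Decrease of >15% from baseline or >30% compared with the last study related measurement in 6MWD"). The row label in SAP Table 4 repeats it. Only the derivation cell of that row differs: "Greater than 30% compared with baseline".

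**Unsatisfactory response.** Protocol 7.1.3 (item 7) reads "Defined as: WHO Functional Class III or IV symptoms with no improvement in 6MWD", and protocol 16.3.3 agrees. SAP 4.3 VII has the same definition: "WHO Functional Class III or IV symptoms with no improvement in 6MWD". SAP Table 14 then derives the 6MWD part as a fall of more than 15%, or more than 30%, both against baseline, which "should be confirmed by repeat measurement performed at least 14 days". SAP 7.6.7 gives the test but no other derivation.

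SAP 11.0, which should list changes from the protocol, is empty, so neither departure is declared as intended.

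**The concern.** Tables 4 and 14 are where the SAP turns these definitions into derivation rules. If Table 4 is programmed as its derivation cell reads, one of the two 6MWD limbs of TTCW disappears. TTCW is second in the alpha-controlled testing order, after 6MWD and before WHO Functional Class. Its time-to-6MWD-decrease component in Table 26 would be affected in the same way.

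If Table 14 is programmed as written, the endpoint changes its meaning. It would count subjects with confirmed deterioration, not subjects who fail to improve. A Class III subject whose walk is unchanged, or 10% shorter, meets the definition but would not be counted. A correction made after unblinding could look data-driven.

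**Working it through.** The plan gives no figure for either point, so there is none to reproduce. The check is logic first, then size under stated assumptions.

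**1. Redundancy of the Table 4 limb.** Let B be baseline, L the last value before the fall and C the current value.
- Table 4: C < 0.85·B or C < 0.70·B. The second condition implies the first, so it adds nothing.
- Definition: C < 0.85·B or C < 0.70·L. The second adds an event when 0.85·B ≤ C < 0.70·L, which requires L > (0.85/0.70)·B = 1.214·B. At B = 300 m that is a prior gain of more than 64 m.

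Example: 300 m at Week 2, then 400, 270 and 265 m.
- The fall is 1 − 270/400 = 32.5% and the repeat is 1 − 265/400 = 33.8% below 400 m. This is an event by the definition if the repeat is judged against the pre-fall value.
- Against baseline the falls are 1 − 270/300 = 10% and 1 − 265/300 = 11.7%. Table 4 records no event.
- If the repeat is judged against the measurement just before it, 1 − 265/270 = 1.9%, and the definition records no event either. No passage says which reference applies.

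**2. Size for TTCW.** This was simulated with 400,000 subjects per scenario.
- Visits: Weeks 6, 10, 14 and 18, with normally distributed changes and equal correlation 0.5 or 0.8.
- Baseline: 250, 300 or 350 m.
- (Mean, SD) of change in metres: (−17, 32), (0, 50), (0, 60), (0, 75), (−17, 60), (30, 60), (52, 42). Together these make 42 scenarios.
- Confirmation: the next visit.

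The SDs of 50 to 75 m match the range in protocol 16.2. The pairs (−17, 32) and (52, 42) are the Phase 2 subgroup results in protocol 5.1. Baselines and correlations are assumptions.

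| Quantity | Result |
|---|---|
| Events added by Table 4's >30% limb | 0 in all 42 scenarios |
| Largest loss, repeat judged against pre-fall value | 29.85% − 27.83% = 2.0% of subjects, or 6.8% of confirmed 6MWD events (mean 0, SD 75, baseline 250 m, correlation 0.5) |
| Same basis, correlation 0.8 | below 0.2% of subjects |
| Largest loss, repeat judged against the measurement just before it | about 0.1% of subjects, 0.4% of events |

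The 2.0% corner is about 0.020 × 150 = 3 subjects. With a mean gain of 30 or 52 m, the relative loss reaches about a tenth of 6MWD events. At mean +52 m, where such events are rare, that is only about 0.08% of subjects.

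**3. Size for Table 14, 6MWD part.** Assume baseline 300 m, mean change 0, SD 50 to 75 m and correlation between Weeks 14 and 18 of 0.5 to 0.8. A 15% fall is 45 m.
- No improvement: P(change ≤ 0) = 0.500.
- Fall of more than 15% at Week 18: Φ(−45/50) = 0.184 to Φ(−45/75) = 0.274.
- Such a fall at both Weeks 14 and 18 (bivariate normal): 0.077 (SD 50, correlation 0.5) to 0.189 (SD 75, correlation 0.8).

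**4. Adding WHO III/IV at Week 18.** The documents give no share, so q = 0.3 to 0.9 is assumed.
- WHO class independent of 6MWD: 0.5q = 15% to 45% meet the definition, against 0.077 × 0.3 = 2% to 0.189 × 0.9 = 17% by Table 14. The ratio runs from 0.5/0.189 = 2.6 to 0.5/0.077 = 6.5 at any q. Per 75-subject arm this is 11 to 34 against 2 to 13.
- WHO class perfectly ordered by 6MWD change: min(q, 0.5) = 30% to 50%, against 8% to 19%.

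**5. Confirmation after Week 18.** Protocol 11.1.5 and Table 2 schedule no 6MWT in Part 1 after Week 18. The next is at Part 2 Week 16, so a fall first seen at Week 18 has no scheduled confirming walk in Part 1.

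**The case against.** The strongest reply concerns weight. The 2.0% loss comes from one corner of 42 scenarios. At baseline 300 m the largest loss is about 1.1%, and under the other reading of the repeat it is about 0.1%. No effect on the log-rank comparison has been shown. Table 4 also carries the correct wording in its own row label, as do Table 3, 7.4.1 and Table 26. A programmer would therefore meet a visible conflict, and loss of the limb is a risk, not a certainty. All of this stands and limits the TTCW half to a small matter. It does not remove the contradiction: SAP 4.2 points to Tables 3 and 4 together without ranking them.

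On Table 14, the endpoint is tertiary with no multiplicity control. The figures show a difference in prevalence at zero mean change, not an effect on the between-arm test. The 2.6-fold floor needs independence; with perfect ordering and q = 0.3 the gap shrinks to 30/19, about 1.6-fold. These limits also stand, but the table still measures a different outcome from the one defined.

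Three further points are fair. The documents do not settle the reference for the confirming repeat, so the firm request is only that it be stated. A numerical cut of change ≤ 0 is the natural reading of no improvement, but it is a proposal. The missing repeat after Week 18 affects the TTCW definition as well as Table 14, although an unscheduled repeat is not ruled out.

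**Conclusion.** The concern holds on both counts. Table 4's second 6MWD limb contradicts every statement of the definition and, as derived, cannot add an event. Table 14 replaces lack of improvement with confirmed deterioration. Neither conclusion depends on an assumption.

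The sizes do. They rest on normal changes, equal correlations, assumed baselines and, for Table 14, an assumed WHO share. On that footing the TTCW loss is at most about 2% of subjects and often close to zero. The unsatisfactory-response count is 2.6 to 6.5 times too low if WHO class is independent of 6MWD, and still clearly too low if it is not. This should be fixed; neither part threatens the primary analysis.

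**What to change.** - **Table 4:** replace the second limb with a fall of more than 30% from the last study-related 6MWD before the fall. State which value the confirming repeat is judged against; using that same pre-fall value is the suggested choice.
- **Table 14:** derive the endpoint as WHO Class III or IV at Week 18 together with a 6MWD change from baseline of zero or less, with no confirmation step.
- **Falls first seen at Week 18:** state how they are handled for TTCW, since no confirming walk is scheduled in Part 1.

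The cost is SAP wording before unblinding. No new data are needed.
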